8.2 EXCLUSION CRITERIA

A subject who meets any of the criteria listed below (in either eye) will be excluded from the study:

1. Use of any of the following medications:
 - a) Restasis or Xiidra within 60 days prior to enrollment;
 - b) Antihistamines (oral or topical) within 10 days prior to enrollment;
 - c) Systemic medication(s) (other than anti-histamines) that is known to cause ocular dryness (e.g. diuretics, anti-hypertensives, anti-depressants, hormone therapy) and whose dose of this medication(s) has not been stable within 30 days prior to enrollment. There must be no anticipated adjustments to the dose of these medications for the duration of the trial;
 - d) Accutane (at any time);
 - e) Oral tetracyclines or azithromycin within 30 days prior to enrollment; or
 - f) Topical ophthalmic antibiotics, anti-glaucoma medications, steroids, non-steroidal anti-inflammatory medications within 30 days prior to enrollment.

NOTE: Use of any of the above medications (with the exception of 1c) is not permitted during the 1 month follow-up period.

2. Any of the following dry eye treatments:
 - a) Office-based dry eye treatment (e.g. IPL, thermal pulsation [Lipiflow], etc.) within 12 months prior to enrollment;
 - b) Meibomian gland expression within 6 months prior to enrollment;
 - c) Blephex or debridement within 3 months prior to enrollment is an exclusion;
 - d) Punctal occlusion or punctal plug placement within 30 days prior to enrollment;
 - e) Use of TrueTear device within the past 2 weeks. (Subjects must refrain from using the TrueTear device for the duration of the study.); or
 - f) Any history of meibomian gland probing
3. History of eyelid, conjunctiva or corneal surgery (including refractive surgery) within the past year. In addition, subjects with any history of the following are excluded: chalazion surgery, surgery on the tarsal conjunctiva, radial keratotomy (RK), complicated blepharoplasty, lid reconstruction, or significant complications post-refractive surgery.
4. Contact lens use within the past 2 weeks. (Subjects must refrain from wearing

contact lenses during the 1 month follow-up.)

5. History of Ocular Herpes Simplex or Ocular Herpes Zoster
6. Any active, clinically significant ocular or peri-ocular infection or inflammation
7. Recurrent clinically significant eye inflammation, other than dry eye, within 3 months prior to enrollment
8. Clinically significant anterior blepharitis. In addition, collarettes or flakes of more than one quarter of the eyelid are excluded.
9. Clinically significant eyelid abnormalities in either eye (e.g. entropion/ectropion, blepharospasm, aponeurotic ptosis, lagophthalmos, distichiasis, trichiasis).
10. Clinically significant dermatologic or cutaneous disease of the eyelid or periocular area.
11. In the clinical judgement of the investigator, meibomian glands have significant capping, atrophy, or are unable to be expressed, digitally or with a sterile cotton swab.
12. Clinically significant ocular surface abnormalities that may affect tear film distribution or treatment (e.g. pterygium, anterior membrane dystrophy, Salzmann's nodules, etc.)
13. Corneal surface abnormalities such as corneal epithelial defects (other than punctate staining), ulcers, corneal epithelial dystrophies, keratoconus, and ectatic disease of the cornea
14. Any active, clinically significant allergic, vernal, or giant papillary conjunctivitis.
15. Ocular trauma within 3 months prior to enrollment.
16. Known history of diminished or abnormal facial, periocular, ocular or corneal sensation
17. Systemic diseases resulting in dry eye (e.g. autoimmune diseases such as Sjogren's syndrome, rheumatoid arthritis, lupus, Graves' disease, sarcoidosis, etc.)
18. Subject is currently using Retin A or Latisse.
19. Subject has permanent eyeliner/lid tattoos, eyelash extensions or wears false eyelashes.
20. Subject is currently using Lash Boost.
21. Allergies to silicone tissue adhesives
22. Participation in another ophthalmic clinical trial within one year prior to enrollment. Subject must also be willing to refrain from another ophthalmic study for the duration of the study.
23. Co-existing condition, either ocular or non-ocular that, in the judgement of the investigator could affect the safety or effectiveness of treatment or the compliance of the subject to the protocol. For example, subjects who are pregnant or nursing or have active, wet macular degeneration are excluded.

9 STUDY PROCEDURES

9.1 STUDY SCHEDULE

Table 3: Study Visit Schedule

Visit (Visit Window)	Baseline (Day -7 to 0)	Treatment ^b (Day 0)	Day 1 (Day 1)	Week 2 (Day 12-16)	1 Mo (Day 21 – 35)
Informed Consent	X ^a				
Demographics, Ocular & Medical History	X				
Medication use	X			X	X
Questionnaires: OSDI, SANDE, Eye Dryness Score	X				X
Manifest Refraction and Best-corrected visual acuity (ETDRS)	X		X ^c	X ^c	X
Slit Lamp Exam	X		X	X	X
Tear Breakup Time	X			X	X
Corneal Staining	X			X	X
Conjunctival Staining	X			X	X
Schirmer 1 Test (without anesthesia)	X				
Meibomian Gland Secretion Scoring	X			X	X
IOP^d	X		X	X	X
Subject Eligibility	X				
Randomization	X				
TearCare or LipiFlow Treatment		X			
AE Assessment	X	X	X	X	X
Discomfort/Pain Questionnaire		X	X		
Collect Eye Drop/Lubricant Log					X

^a Subjects may sign the informed consent up to 30 days in advance of the baseline visit.

^b The TearCare or LipiFlow treatment must be performed within 7 calendar days of the Baseline visit. If scheduling permits, it may be performed on the same day as the Baseline visit following Randomization. Refer to Section 9.5.1 for details.

^c On Day 1 and Week 2, Best Corrected Spectacle Visual Acuity (BCSVA using EDTRS) is measured without manifest refraction (MR). If the VA has worsened by ≥ 10 letters (per ETDRS) from baseline, then MR should be performed, the ETDRS measurement should be repeated, and the VA post-MR should be recorded.

^d IOP measured via applanation tonometry should be measured at baseline using standard of practice at each site with the same method to be used for all consecutive visits in the study.

9.2 NUMBER OF SUBJECTS, DURATION OF FOLLOW-UP AND STUDY DURATION

A total of up to 238 subjects will be enrolled and randomized in the study. Assuming a 15% screen failure rate, approximately 278 subjects will be enrolled and screened to obtain up to 100 randomized subjects using the initial SmartLid design (Cohort 1) and

138 randomized subjects using the modified SmartLid design (Cohort 2). All subjects will be followed for 1 month.

It is anticipated that enrollment in the study will take 8-11 months. Including the 1-month follow-up period, the study is expected to last 9-12 months.

9.3 MATERIAL AND EQUIPMENT

A listing of general equipment and materials required at the investigational site for the study is provided below.

- TearCare System (including a SmartHub, SmartHub Nest, and charging adapter)
- TearCare SmartLid Devices and Clearance Assistant Devices
- LipiFlow System and Activators
- ETDRS Visual Acuity System
- Slit lamp
- Wratten filter (yellow) (for corneal staining)
- Goldmann Tonometer or other applanation tonometer
- Meibomian Gland Evaluator (TearScience, Inc.)
- Fluorescein sodium strips (for TBUT and corneal staining)
- Lissamine green strips (for conjunctival staining)
- Filter strips (for the Schirmer test)
- 2-20 μ L & 20-200 μ L micropipettes and sterile tips
- Microcentrifuge tubes
- Preservative-free sterile saline
- Proparacaine 0.5% or tetracaine 0.5% ophthalmic drops
- Akten® (lidocaine hydrochloride ophthalmic gel) 3.5% or equivalent
- Stopwatch
- Ruler
- Makeup remover wipes
- Sterile scissors

9.4 INFORMED CONSENT AND POINT OF ENROLLMENT

The IRB-approved informed consent will be presented and explained to each prospective subject by the investigator or a trained clinical professional. Once the subject has had ample time to read the consent form, has been informed of all aspects of the study, and has had an opportunity to ask questions, the subject will be given a choice to voluntarily confirm his or her participation in the study as documented by completion of the Informed Consent. After signing the Informed Consent and the HIPAA (Health Insurance Portability and Accountability Act) authorization, the subject can then proceed with the baseline visit. The baseline visit should be performed within 30 days

of the subject signing the informed consent. The subject has the right to withdraw from the study at any time without consequences, as indicated in the Informed Consent Document.

The subject's signed and dated informed consent must be obtained before conducting any procedure specifically for the study. Subjects are enrolled upon signing the ICD even if they subsequently fail to meet the eligibility criteria.

The principal investigator(s) must retain the original, signed written Informed Consent Document. A copy of the written Informed Consent Document must be given to the subject.

9.5 BASELINE AND TREATMENT VISIT(S)

9.5.1 SCHEDULING THE BASELINE AND TREATMENT VISIT(S)

To facilitate scheduling, the Baseline and Treatment Visits may be performed in the same day or on two separate days. If these visits are performed over two days, the Treatment Visit must be within 7 calendar days of the Baseline Visit. For follow-up scheduling purposes, the date of the Treatment Visit is Day 0.

Refer to Table 3 for which tests and exams are to be performed in each visit. Endpoint assessments performed during the Baseline visit must be performed by a Masked Assessor (See Section 9.7).

Since dry eye drops and lubricants can affect the endpoint assessments, instruct subjects not to use any of these products within 2 hours of the Baseline visit.

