8 STUDY SELECTION CRITERIA

8.1 INCLUSION CRITERIA

For inclusion in this study, subjects must meet all of the following criteria:

1. At least 22 years of age
2. Reports dry eye symptoms within the past 3 months
3. Reports having to use artificial tears or lubricants regularly over the past month to relieve dry eye symptoms.
4. OSDI Score of 23-79
5. TBUT of ≤ 7 seconds in both eyes
6. Meibomian gland obstruction in both eyes based on a total Meibomian Gland Secretion Score ≤ 12 in each eye.
7. At least 15 glands in each lower eyelid should be expressible, with a sterile cotton swab, at the slit lamp.

8. Best corrected visual acuity of 20/100 or better in both eyes.
9. Willing and able to comply with the study procedures and follow-up
10. Willing and able to provide informed consent
11. English-speaking

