9.5.6 FOLLOW-UP INSTRUCTIONS FOR SUBJECTS

Review the following instructions with subjects at the completion of the visit.

During the 1 month follow-up:

1. Dry Eye Lubricants/Drops: Subjects should make every effort to refrain from using any dry eye drops, lubricants, or other type of dry eye treatment (e.g. warm compresses, prescription medication, etc.). If they require “rescue therapy” to relieve their symptoms, they should use the same type of drops or lubricants they were using prior to the study.
2. Dry Eye Lubricant/Drop Log: Provide subjects with the Lubricant/Drop log and instruct them to record any use of drops or lubricants during the follow-up period.
3. Other Dry Eye Medications: Subjects should not use any other medications for dry eye disease (e.g. Restasis, Xiidra, etc.)
4. Other Treatments for Dry Eyes: Subject should not have any other treatments for dry eyes. For example, they should not use warm compresses or perform lid

massage. They should not use the True Tear device or have any other in-office dry eye treatments.

5. Anti-histamines: Subjects should not use any anti-histamines.

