9.6 FOLLOW-UP VISITS

Prior to the Visit: Reminder Call

A few days before the follow-up visit, it is recommended that the coordinator contact the subject to remind them not to use dry eye drops or lubricants on the day of the follow-up visit since these products can affect the endpoint assessments.

At the Beginning of the Follow-up Visit: Maintaining Masking of Study Personnel

Endpoint assessments performed during the Follow-up visit must be performed by the Masked Assessor (See Section 9.7).

At the beginning of the follow-up visit, the coordinator should remind the subject to not reveal their randomization group to the study personnel who will be performing the follow-up exams.

Order of Procedures During the Follow-Up Visit

Follow-up procedures will be performed per the Study Schedule provided in Table 3 (page 30) and the methods included in Appendix A. Since certain tests/exams can impact the ability to perform other tests/exams, the following tests and exams should be performed in this order:

1. Questionnaires
2. Manifest refraction, if required per this protocol, and ETDRS Best-corrected visual acuity
3. Slit Lamp Exam
4. Tear Breakup Time
5. Corneal staining
6. Conjunctival staining
7. Meibomian Gland Secretion Scoring

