12.5.6 SECONDARY EFFECTIVENESS ENDPOINTS

The secondary effectiveness endpoints include change from baseline for the following outcomes:

1. Ocular Surface Disease Index (OSDI) score
2. Corneal staining scores
3. Conjunctival staining scores
4. Symptom Assessment iN Dry Eye (SANDE) scores
5. Eye Dryness Score
6. Number of Meibomian Glands Yielding any liquid
7. Number of Meibomian Glands Yielding clear liquid

If both primary effectiveness hypotheses are both met for the Cohort 2 per-protocol population, then we will sequentially test each of the secondary effectiveness endpoints based on the Cohort 2 per-protocol population to determine whether there is a significant change between baseline and 1 month. In each case we will test the null hypothesis that the change is 0 against the appropriate alternative (depending on the favorable direction). All testing of the secondary endpoints will be done using a two-sided alpha of 0.05. We will test the secondary endpoints in the order listed, stopping at the point where a test fails to reject. This sequential procedure controls the overall type I error rate for the secondary endpoints.

The secondary endpoints can be divided into two groups, those which are measured on a per-eye basis (Corneal Staining, Conjunctival Staining, Meibomian gland scores) and those measured on a per-subject basis (OSDI Score, SANDE Scores, Eye Dryness Score).

The per-eye secondary endpoints (Corneal Staining, Conjunctival Staining, Meibomian gland counts) will be tested using a similar linear mixed effects modeling approach as for the primary endpoint, with treatment as a fixed effect, and including a random intercept per subject to account for correlation.

The per-subject secondary endpoints (OSDI score, SANDE scores, Eye Dryness Score) are measured at the subject level so there is only one measurement per subject. For these endpoints a paired t-test will be used to evaluate change from baseline to 1 month.

The secondary effectiveness outcomes of the Cohort 1 per-protocol population will be summarized separately by descriptive statistics (mean, median, standard deviation,

minimum, and maximum for the continuous variables; count and percent for the categorical outcomes).

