22 APPENDIX B – STATISTICAL ANALYSIS PLAN

22.1 EFFECTIVENESS ENDPOINTS AND ANALYSIS METHODS

22.1.1 PRIMARY EFFECTIVENESS ENDPOINT

The primary effectiveness endpoints are the change from baseline in Tear Break-Up Time (TBUT) and the total Meibomian gland secretion score (MEIB) at the 1 month follow up. Change is calculated as: 1 month – baseline, so a positive change is better. Both endpoints will be analyzed using a linear mixed effects (LME) model. This will allow for the proper incorporation of within-person correlation into the statistical tests, and will also allow for adjustment for baseline measurements. Both of these should increase the power over the simple “t-test using one eye” approach.

Since the SmartLid device was modified during the trial, all effectiveness analyses will be carried out with the Cohort 2 subjects only (i.e. subjects enrolled after the modified device was introduced). The primary effectiveness outcomes of the Cohort 1 subjects will be summarized separately by descriptive statistics (mean, median, standard deviation, minimum, and maximum).

The linear mixed effects model for TBUT can be written as follows:

$$y_{ij} = \beta_0 + \beta_1 T_i + \beta_2 TBUT_{ij,0} + b_{0i} + \epsilon_{ij}$$

Where

- $TBUT_{ij,k}$ is the TBUT value for subject i , eye j , week k .
- y_{ij} is the 1 month change from baseline TBUT for subject i , eye j .
$$y_{ij} = TBUT_{ij,4} - TBUT_{ij,0}$$
- T_i is the binary treatment indicator for subject i (0 = LipiFlow, 1 = TearCare)
- β_0, β_1 , and β_2 are the fixed effect parameters:
 - β_0 is the mean change from baseline for the LipiFlow arm,
 - β_1 is the difference between TearCare and LipiFlow in mean change from baseline,
 - β_2 is the effect of each unit change in baseline TBUT.
- b_{0i} is the random effect (random intercept term) for subject i
$$b_{0i} \sim N(0, \sigma_a^2)$$
- ϵ_{ij} is the normally-distributed error term
$$\epsilon_{ij} \sim N(0, \sigma_e^2)$$
- $\{b_{0i}\}$ and $\{\epsilon_{ij}\}$ are independent

To demonstrate non-inferiority of the TearCare treatment to the LipiFlow control for TBUT we will test the null hypothesis that β_1 is less than the non-inferiority margin of 3 seconds:

$$H_0: \beta_1 \leq -3.0$$

$$H_A: \beta_1 > -3.0$$

That is, we seek to reject the non-inferiority null hypothesis that the TearCare change in TBUT is more than 3 seconds worse than the LipiFlow change in TBUT.

For this model there are several equivalent ways to carry out this test:

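### The lubricant-free rule differs between Baseline and follow-up, so the secondary tests of change against zero include a shift in measurement conditions of unknown size and direction; the primary between-arm contrast is not biased by it

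*Combined protocol and SAP*

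**What the plan says.** Section 9.5.1 opens its instruction with "Since dry eye drops and lubricants can affect the endpoint assessments" and tells sites to "instruct subjects not to use any of these products within 2 hours of the Baseline visit".

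Section 9.6 repeats that reason but sets a different restriction, given as the content of a telephone reminder: "remind them not to use dry eye drops or lubricants on the day of the follow-up visit". It is also weaker in form. The call is made a few days ahead and is not required; the wording is "it is recommended that the coordinator contact the subject".

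Three other parts of the plan bear on this:

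- **Background use.** Entry requires a subject who "Reports having to use artificial tears or lubricants regularly over the past month to relieve dry eye symptoms" (section 8.1, criterion 3). After treatment, "Subjects should make every effort to refrain from using any dry eye drops, lubricants, or other type of dry eye treatment" (section 9.5.6); rescue use is allowed and logged (sections 9.5.6 and 9.9).
- **Primary analysis.** The tested parameter β1 "is the difference between TearCare and LipiFlow in mean change from baseline" (SAP section 22.1.1), with the baseline value as covariate.
- **Secondary analysis.** If both primary hypotheses are met, the seven secondary endpoints are tested in order, and for each "we will test the null hypothesis that the change is 0 against the appropriate alternative" (section 12.5.6). OSDI, SANDE and Eye Dryness Score use a paired t-test.

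Lubricant use is summarised by arm (sections 12.5.1 and 12.5.7). No analysis uses the time since the last drop.

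**The concern.** The protocol treats lubricants as something that disturbs the measurements, then controls them differently at the two time points whose difference is tested. A subject who used drops on the morning of an afternoon Baseline visit complies with section 9.5.1; the same use before a follow-up visit goes against the section 9.6 reminder.

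Where a test compares change with zero, no control arm removes such a shift. The secondary endpoints supply all the symptom evidence, because both primary endpoints are signs (section 6.1), and the indication sought covers signs and symptoms (section 2). If part of a secondary change reflects different conditions, the test cannot separate that part from the effect of treatment.

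**Working it through.** **1. The two rules side by side**

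| | Baseline (9.5.1) | Follow-up (9.6) |
|---|---|---|
| Restriction | none within 2 hours of the visit | none on the day of the visit |
| Form | instruction to subjects | recommended reminder call |
| Reason | can affect endpoint assessments | the same |
| Arms | both | both |

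If the day is assumed to run from midnight, the follow-up rule implies at least 9 hours for a 9 am visit and 16 hours for a 4 pm visit, against at least 2 hours at Baseline.

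**2. Where a shift goes.** Let τ be the true mean change in an arm and δ the shift due to the differing rules.

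- Within an arm: expected observed change = τ + δ.
- Between arms: (τ_TearCare + δ) − (τ_LipiFlow + δ) = τ_TearCare − τ_LipiFlow.

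A common δ therefore drops out of the primary contrast and stays in full in any within-arm change.

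**3. The plan's own sample size.** No planned figure is in dispute. For TBUT (margin 3.0 s, SD 6.0 s, one-sided α 0.05, power 95%), the normal formula gives 2 × 6² × (1.645 + 1.645)² / 3² = 86.6, so 87 eyes per arm. The noncentral t gives 88, or 176 in total, as stated. Then 176 × 1.4 = 246.4; 246.4 / 0.9 = 273.8, rounded to 274 eyes, or 137 subjects. This reproduces SAP section 22.3.1.

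**4. Primary test under an assumed common shift.** Inputs: 69 × 0.9 ≈ 62 completers per arm; SD 6 s; intraclass correlation 1.92 / (1.92 + 3.39) = 0.36; subject means of two eyes; 20,000 simulated trials.

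| Common follow-up shift | True difference | Mean between-arm difference | Non-inferiority concluded |
|---|---|---|---|
| 0 s | 0 | −0.01 s | 95.5% |
| −1 s | 0 | −0.01 s | 95.7% |
| +1 s | 0 | 0.00 s | 95.8% |
| +2 s | 0 | 0.00 s | 95.7% |
| 0 s | −3 s | −2.99 s | 5.0% |
| +1 s | −3 s | −3.01 s | 4.9% |
| +2 s | −3 s | −3.00 s | 4.9% |

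Power and type I error do not move beyond simulation error. The TearCare mean change moves one for one with the shift: 2.0, 3.0, 4.0 and 5.0 s for shifts of −1, 0, +1 and +2 s when the true difference is 0.

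**5. Change-versus-zero test when the only change is δ.** Two-sided 0.05 paired t-test, noncentrality (δ/SD) × √n. The documents give no δ, so these values are assumed. Section 12.5.6 does not say whether the arms are pooled, so both cases are shown.

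| δ / SD | n = 124 (pooled) | n = 62 (one arm) |
|---|---|---|
| 0.1 | 20% | 12% |
| 0.2 | 60% | 34% |
| 0.3 | 91% | 64% |
| 0.5 | 100% | 97% |

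For example, 0.2 × √124 = 2.23. These are two-sided rejection rates. They show how sensitive the test is to a shift, not that the shift favours a claim of benefit. With a real effect the noncentrality is (τ + δ)√n / SD, so a δ against improvement lowers power instead.

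**The case against.** The strongest reply is that this is a wording mismatch with no demonstrated size or harmful direction. Four parts of it stand.

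- **Direction.** If a recent drop makes Baseline look better, the stricter follow-up rule shrinks the measured improvement, and the tests against zero become conservative.
- **Extent.** Criterion 3 gives no frequency, and 2 hours is a minimum. A subject with a morning visit may satisfy both rules. A reader might infer that nearly everyone was affected at Baseline; the documents do not show how many used drops that day.
- **Which endpoints.** Five of the seven secondary endpoints are questionnaires (OSDI, SANDE, Eye Dryness) or gland counts obtained by pressing on the lid. The documents do not say which assessments lubricants affect, or by how much.
- **The larger contrast is planned.** Regular use before entry and a month of intended abstention afterwards would differ even with identical visit rules.

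A reader might also infer that every change-from-baseline result, including the primary comparison, is contaminated. The documents do not support that: β1 is a randomised difference under visit rules common to both arms. Actual lubricant use could still differ by arm, because subjects are unmasked (section 7) and rescue use is allowed. Assumed unequal shifts would then matter: +1.0 s for TearCare and +0.5 s for LipiFlow give a type I error of 13.8%, and the reverse gives power of 87.6%. That would come from behaviour after randomisation, not from the mismatch between 9.5.1 and 9.6.

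For the per-eye secondary endpoints, the model includes treatment as a fixed effect, so an arm difference could be read from it. The stated null nevertheless concerns change from baseline, and the per-subject endpoints have only the paired test.

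**Conclusion.** The point holds for within-arm change only. Sections 9.5.1 and 9.6 set different restrictions for the same stated reason, and the secondary tests against zero include whatever shift results. Its size and sign cannot be estimated from the documents; the 60% to 91% range rests on an assumed pure shift of 0.2 to 0.3 SD with 124 subjects pooled.

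The mismatch does not bias the primary non-inferiority conclusion, provided the rules act equally in both arms. The baseline covariate and the eligibility measurements are taken under the shorter minimum interval, but again alike in both arms. This is a low-severity point, worth acting on because the remedy is cheap.

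**What to change.** Reconcile sections 9.5.1 and 9.6 so that one lubricant-free interval, stated with the same force, applies before the Baseline, Week 2 and Month 1 assessments. The choice of interval is the sponsor's. Record the time of last lubricant use at each of these visits. Medication use is already collected at all three and the drop log at Month 1 (Table 3), so the only new item is time since last use.

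The cost is a short amendment, with IRB review as necessary (section 15), a site reminder and one data field. The sample size of 138 does not change. The study was already under way when the device was modified (section 4.4), so a mid-study change would leave some subjects measured under the present rules; the report should say which.

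The fix is partial. Regular use before entry against abstention during follow-up remains, so within-arm secondary changes should still be interpreted with that in mind.
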